5.0 Study Procedures

5.1 Study Design

This study will consist of two parts. Part 1 is diagnostic in nature, whereas Part 2 is a preliminary treatment study that will include a portion of the participants from Part 1.

Part 1 Procedures

The participants completing this study will be veterans between the ages of 20 and 50 years and divided into 4 groups: 2 groups of 117 veterans who report histories of blast exposure and blast-related clinical signs consistent with the VA/DoD definition of mTBI (VA/DoD, 2009) and present with normal or near normal results on standard audiometric testing but who report substantive problems with audition; a group of 117 normal hearing controls who report no auditory problems and no histories of blast exposure, brain injury, or psychiatric disorder (Normal Controls); and a group of 117 normal hearing veterans with PTSD and no blast exposure or blast-related clinical signs (PTSD-only). Of the two groups of veterans with auditory complaints one group will present with little or no PTSD (mTBI-only), whereas the other group will be symptomatic for PTSD (mTBI+PTSD). A total of 468 participants will complete the study and 50 additional participants will be allowed for experimental attrition.

In addition to the 468 veteran participants, 468 family members or friends (significant others) will complete a questionnaire about the veterans' hearing handicap.

After a telephone screen and preliminary testing, a battery of behavioral and physiological measures will be administered to all 4 groups of veterans to characterize the level and nature of their auditory impairments. Included are tests and procedures that likely will capture underlying or related problems and are commonly used in clinical and experimental studies of the peripheral auditory system, central auditory processing disorders, speech and language perception in noise, and executive function in persons with brain injury.

Interested veterans will first be screened by telephone. For those veterans who pass the screen, the testing (preliminary and experimental) will be conducted across multiple sessions at one of the study sites. The first session will include the preliminary measures such as standard audiometric tests, questionnaires, and a vision screen to ensure appropriate inclusion and exclusion of participants. The subsequent experimental sessions will include additional questionnaires and assessment procedures. It is estimated that the preliminary and experimental testing will require about 8 to 12 hours, with the total time dependent on patient characteristics (e.g., fatigue, response speed, need for breaks, task tolerance). It is anticipated that most participants will be able to complete all of the procedures in Part 1 within 4 to 5 sessions, but 4 additional sessions will be allowed if more time, shorter sessions, or frequent breaks are needed. Our clinical experience with the targeted populations is that 2 to 3 hour sessions are tolerated well and not burdensome. [name] et al. (2011) used a similar battery and test burden was not mentioned as a factor in their publication.

Telephone Screen – After describing the study to prospective veteran participants, those who remain interested in participating will be asked a series of screening questions to ensure that they are within the targeted age range, can read and write well enough to complete the tasks, have no prior history of hearing aid use, have brain injury or disorder within the severity range targeted by the study, and whether they can be paid by direct deposit. Veterans passing the telephone screen and who wear corrective lenses will be asked to bring their glasses or contacts to the subsequent sessions so they will be able to complete forms, the Snellen screen, questionnaires, and other tasks involving visual processing.

Preliminary Tests – Preliminary assessment procedures will be administered to determine group placement and exclude participants who might have difficulty completing the study. The procedures include the following:

- a. A case history that includes questions targeting hearing, tinnitus, blast exposure, concussion, brain injury, PTSD, headache, pain, communication problems, academic histories, employment status and other demographic data (Attached).
- b. Brief Traumatic Brain Injury Screen (BTBIS; Schwab et al., 2006) to determine probable mTBI
- c. PTSD Checklist-Military Version (PCL-M: National Center for PTSD-Behavioral Division; Weathers et al., 1994) to screen for PTSD
- d. Hearing Handicap Inventory in Adults (HHIA, Newman et al., 1993) to document self-perceived hearing handicap. It will be administered at the beginning and end of Part 1 to document baseline handicap status prior implementing Part 2 of the study.
- e. A standard audiometric hearing test battery that includes otoscopy, tympanometry, and an acoustic reflex screen at 1000 Hz, air- and bone-conduction pure-tone threshold testing (ASHA, 2005), and the Northwestern University Test # 6 (NU-6; Tillman & Carhart, 1966)
- f. Loudness discomfort levels (LDLs) for tones at 500, 1000, 2000 and 4000 Hz according to procedures recommended by Sherlock and Formby (2005) to document hyperacusis
- g. Snellen chart to screen vision

- h. Motor-Free Visual Perception Test, version 4 (MVPT-4) to document that the subjects have the basic visual processing skills to perform tasks that include visual stimuli

Table 1. Group inclusion criteria based on preliminary test measures.

PRELIMINARY ASSESSMENT	GROUPS			
	mTBI-only	mTBI+PTSD	PTSD-only	Normal Controls
Blast Exposure History	Yes	Yes	No	No
Normal or Near Normal Standard Audiometric Test Results	Yes	Yes	Yes	Yes
History of Wearing Hearing Aids Consistently	No	No	No	No
BTI	Evidence of Brain Injury	Evidence of Brain Injury	No Evidence of Brain Injury	No Evidence of Brain Injury
PCL-M	≤ 20	> 20	> 20	≤ 20
HHIE	> 16	> 16	Not considered	≤ 16
LDLs	No Hyperacusis	No Hyperacusis	No Hyperacusis	No Hyperacusis
Snellen (corrected or uncorrected)	20/30	20/30	20/30	20/30
MVPT-4	$> 5^{\text{th}}$ percentile	$> 5^{\text{th}}$ percentile	$> 5^{\text{th}}$ percentile	$> 5^{\text{th}}$ percentile

Experiment Procedures

Part 1 Procedures

The experimental procedures are listed below according to type of assessment. Most are commonly used clinical procedures and will be completed in the standard manner.

Health and Quality of Life Questionnaires –

- a. World Health Organization Disability Assessment Schedule II (WHODAS II) as a measure of general health status and quality of life (McArdle et al., 2005)
- b. Satisfaction with Life Scale (SWLS) to document health-related quality of life
- c. Brief Symptom Inventory-18 Item (BSI-18) to document self-perceived psychiatric and psychological status
- d. The Speech, Spatial and Qualities of Hearing Scale (SSQ; Gatehouse & Noble, 2004) to assess self-perceived functional and situational auditory skills not covered by the other questionnaires. Like the HHIA, the SSQ will be presented at the beginning and end of Part 1 to establish the pretreatment baseline for Part 2.
- e. The Tinnitus Functional Index (TFI; Meikle et al., 2012) will be administered because many patients with mTBI and PTSD complain of tinnitus and it can impact perceived handicap and quality of life (Fagelson, 2007), although it should be noted that in our chart review of the target population tinnitus was not a primary complaint with only 21.7% reporting any tinnitus.
- f. The Hearing Handicap Inventory for Adults-Significant Other (HHIA-SO; Newman & Weinstein, 1988) will be completed by a significant family member or friend (if available) to capture auditory-related problems noticed by others but not by the participants. The veteran will give the questionnaire to a family member or friend to complete and mail to the study site. These data will be kept confidential from the veteran, and the family members or friends can refuse to participate by not completing or mailing the questionnaire.
- g. HHIA will be repeated to document stability of handicap.
- h. Information about general medical history, blast and head injury, neurological history; audiology assessment history and behavioral health diagnosis and treatment history also will be collected from the VA Computerized Patient Record System (CPRS) to confirm status.

Peripheral Auditory System –

- a. Distortion product otoacoustic emission (DPOAE) to assess cochlear integrity
- b. Fast Psychophysical Tuning Curves (FPTC) to determine filtering and spectral tuning properties of each ear. The fast tuning curves will be obtained for 2000 and 4000 Hz signals using the procedures and software developed by Sek and Moore (2011).
- c. Temporal Fine Structure 1 test (TFS1; Moore & Sek, 2009) to assess the ability of the cochlea to process fine acoustic structures.

Central Auditory System –

- a. Tonal and speech Masking Level Difference (MLD) tests according to procedures described by (Wilson et al, 2003; Wilson et al., 1994).
- b. Competing Sentences subtest from the SCAN-3A to measure the ability to focus on a primary speech signal and ignore background speech
- c. Two-digits section of the Dichotic Digits Test (DDT; Musiek, 1983) to assess dichotic auditory function

- d. Staggered Spondaic Word Test (SSW) to measure timing and inter-hemispheric processing of words
- e. Gaps in Noise Test (GIN) to assess temporal processing in noise
- f. Auditory brainstem response (ABR), middle latency response (MLR), long-latency response (LLR) and active event-related P300 to assess the electrophysiological status of the central auditory system.

Speech and Language Processing in Noise –

- a. The Words-in-Noise test (WIN; VA Compact Disk 4.0; Wilson & Burk, 2005) to target listening at the single word level
- b. The Listening in Spatialized Noise - Sentences Test (LiSN-S; Cameron & Dillion, 2012) to assess sentence perception in noise within a simulated 3-dimensional acoustic space
- c. Auditory and reading versions of subtests 1 through 10 from the Computerized Revised Token Test (CRTT and CRTT-R respectively; McNeil et al., 2009) will be administered in quiet and in +3 dB signal-to-babble to assess sentence level processing in both auditory and reading domains. The preliminary CRTT pretests will be administered prior to these tests to assure that the participants have the basic skills to complete the tasks and to measure baseline reaction time.

Executive Function –

- a. Digit span forwards and backwards both acoustically and visually according to Kemtes and Allen (2008) to assess verbal short term and computational memory skills
- b. The CRTT Stroop task (CRTT-R-Stroop; McNeil et al., 2010) to assess the interaction between language and executive function
- c. Rey Auditory Verbal Learning Test (Schmidt, 1996) to assess immediate and delayed verbal memory, efficiency of learning and the effects of interference
- d. Trail Making Test (Reitan, 1992) to measure attention and processing speed

PART 2 Procedures

Hearing Aid Fittings (treatment groups) – In Part 2 a subset of the participants from the mTBI-only and mTBI+PTSD groups from Part 1 will be fitted binaurally with open-fit hearing aids with mild high-frequency gain. Each group will consist of 25 participants. They will be randomly selected and randomly replaced if they decline to participate at any point during the treatment protocol.

Standardized fitting and verification procedures consistent with the American Academy of Audiology guidelines for audiology management of adult patients will be used. The hearing aids will be obtained through the VA hearing aid procurement procedures because the participants qualify for hearing aids due to their auditory impairment. High-end behind-the-ear hearing aids (Phonak Bolero Q90) will be fitted binaurally. The hearing aids will provide mild gain with high-frequency emphasis, which will be verified acoustically with real ear measures. The noise suppression circuitry of the hearing aids will be activated but the frequency compression or shifting will be deactivated.

Additionally, to reduce the risk of sounds being too loud for the participants, Maximum Power Output will be set below the loudness discomfort levels of the participants.

Prior to their hearing aid fitting the participants in the two treatment groups will complete the unaided portion of the Abbreviated Profile of Hearing Aid Benefit (APHAB, Cox & Alexander, 1995), along with the HHIA, and SSQ as pretreatment measures of self-perceived hearing handicap, and situational hearing skills. To assess pre-fitting speech perception and language processing the California Consonant Test (CCT; Owens & Schubert, 1997) will be administered in the sound field at 65 dB HL in quiet and with multi-talker babble.

Recovery of co-articulation (phonetic context effect) will be measured with a vowel identification task. The vowels will be presented in the context of /d/ and /b/ sounds (Holte & Lotto, 2006). The extent to which the consonant context changes the perception of vowel categories will be measured.

As in Part 1 of the study, sentence level processing will be measured with the auditory and reading versions of subtests 1 through 10 from the Computerized Revised Token Test (CRTT and CRTT-R respectively) and will be administered in quiet and in babble to assess sentence level processing in both auditory and reading domains in optimal and adverse acoustic conditions.

Follow-up Testing – The participants will be followed over a 6-month period. One week (+/- 3 days) after the fitting the participants will be seen in the lab to re-verify the fit of their hearing aids and to determine any problems. The hearing aid use-time will be recorded from the data-logging system of the hearing aids as a reflection of hearing aid benefit and to document the extent to which the participants are wearing their hearing aids. During this session, both the aided and unaided portions of the APHAB will be administered along with the International Outcomes Inventory for Hearing Aids (IOI-HA; Cox & Alexander, 2002). In addition, the participants will answer a single question about their likelihood to continue hearing aid use. Intent to continue use tends to be related to user satisfaction with commercial products and service provision in other areas of healthcare. The participants also will complete the HHIA, and SSQ. The CCT, CRTT, CRTT-R and the phonetic context effect tasks will be re-administered with and without hearing aids.

Home Visits – The participants will be visited in their homes by study staff at three different times: 1-, 2- and 4-months post-fitting (+/- 1 week). The home visits will occur to reduce participant burden and encourage retention. However, some participants might prefer to be seen in the lab or clinic than their homes, and if that is the case those participants will be accommodated. Hearing aid use-time will be recorded from the data-logging system of the hearing aids and the hearing aids will be checked to determine appropriate function. During these visits the HHIA, SSQ, APHAB, IOI-HA, and the intent to continue use question will be re-administered. New hearing aid batteries will be provided and participants will be encouraged to wear their hearing aids for longer periods of time if their use-time is below 8 hours a day. At 6-months post-fitting (+/- 1 week) the laboratory follow-up testing will be repeated.

Delayed-Treatment Control Group – The participants in the delayed-treatment control group will be selected from the mTBI-only group and followed over a 12-month period (+/- 2 weeks). At the onset of Part 2 they will complete the HHIA, SSQ, and the unaided portion of the APHAB. They will complete the speech perception and language tasks administered to the treatment group (CCT, phonetic context effect, and CRTT tasks) but unaided only. The delayed-treatment groups will receive home visits at 1, 2, 4 months (+/- 1 week) post-entry, at which times they will complete the HHIA, SSQ, and the unaided portion of the APHAB. At 6 months post-entry their pure tone hearing thresholds will be measured to determine possible changes in hearing sensitivity, and the procedures used with the treatment groups will be applied with the same sequence of follow-up sessions.

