- b. Are certain test procedures and stimuli particularly sensitive to the deficits found with this population of veterans and are deficit patterns influenced by the coexistence of PTSD?
- c. Does the addition of background noise produce over-additive effects in this population of veterans and does PTSD increase the effect?
- d. Does this population of veterans perceive and demonstrate benefit when fitted with hearing aids that provide mild high-frequency gain and does PTSD influence benefit?
- e. Is hearing aid benefit predictable by measures of auditory processing, speech perception, psychoacoustic, verbal working memory, and language processing? Furthermore, does the coexistence of PTSD influence the relationship between these measures and hearing aid benefit?

Expected Outcomes

- a. This population of veterans will differ from veterans with no history of blast exposure, and the presence of PTSD will increase severity and alter the deficit pattern.
- b. This population of veterans will experience significant problems with the addition of background noise and the effect will be influenced by linguistic load, verbal working memory and attention.
- c. This population of veterans will demonstrate and perceive benefit from being fitted with mild-gain high-frequency hearing aids, although the coexistence of PTSD will restrict perceived benefit.
- d. Mild-gain high-frequency amplification will improve speech perception skills in quiet and noise, and improve linguistic processing and executive function.
- e. Benefit from amplification will relate to the deficits that the veterans present.

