Primary Analyses – Basic descriptive statistics will be computed and examination of statistical assumptions will be performed for all study measurements. For questionnaire data, analysis of variance (ANOVA) or Kruskal Wallis test will be used to determine differences in the overall and subset scores between the mTBI groups. The analysis will also include basic descriptive statistics for behavioral data test measures at baseline and at 6 months for the mTBI-only and mTBI+PTSD groups, and at baseline and 12 months for the delayed-treatment groups. We will focus on the changes in the behavioral test measures from baseline to 6 months (mTBI-only and mTBI+PTSD treatment groups) and from baseline to 12 months (delayed-treatment groups). Specifically, paired t-test or Wilcoxon signed rank test will be used to determine change at 6 or 12 months and this test will be applied to each behavioral test measure separately. False discovery rate will be used to adjust the p-values for multiple hypotheses testing. All statistical analyses will be two sided and the significance level will be 0.05.

Secondary Analyses – For longitudinal analysis, the data will be modeled using linear-mixed models for which the outcome is the behavioral test measure across time. The predictors will include time, group and interaction between group and time. Covariates will be added to the model as needed. In addition, variables with a high Gini score from Part 1 will be correlated with final hearing aid results as a preliminary investigation of whether hearing aid benefit can be associated by any of the variables obtained above. We will measure correlations using either Pearson's or Spearman's correlation coefficient. We will adjust the p-values for multiple testing by using a false discovery rate method whenever more than one variable is being tested. Single-subject design metric also will be used to investigate individual responses to the hearing aid treatment.

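### The Part 2 behavioural tests cannot separate amplification from retest practice, and no inferential test of the same-visit aided-minus-unaided difference is specified

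*Combined protocol and SAP*

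**What the plan says.** Section 3.0 (Expected Outcomes, item d) predicts that "Mild-gain high-frequency amplification will improve speech perception skills in quiet and noise", along with gains in linguistic processing and executive function. Question d in the same section asks whether these veterans show benefit from the aids.

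Section 5.1 (Part 2 Procedures) sets the testing. Treated participants take the CCT, a vowel-identification (phonetic context) task and the CRTT and CRTT-R before fitting; for the last two, "As in Part 1 of the study, sentence level processing will be measured with the auditory and reading versions". At 1 week, "The CCT, CRTT, CRTT-R and the phonetic context effect tasks will be re-administered with and without hearing aids". At the home visits in months 1, 2 and 4 only questionnaires are given: "During these visits the HHIA, SSQ, APHAB, IOI-HA, and the intent to continue use question will be re-administered". Then "At 6-months post-fitting (+/- 1 week) the laboratory follow-up testing will be repeated".

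Delayed participants take the behavioural tasks once at entry, unaided. Their visits at months 1, 2 and 4 also carry questionnaires only, "at which times they will complete the HHIA, SSQ, and the unaided portion of the APHAB". At month 6 the section lists pure-tone thresholds and then applies the treated groups' procedures and follow-up sequence. A second pre-fitting battery at that point is implied but not spelled out.

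Section 5.6 (Part 2 Analysis, Primary Analyses) states "We will focus on the changes in the behavioral test measures from baseline to 6 months" for the treated groups and to 12 months for the delayed groups, tested within group by paired t or signed-rank test with false-discovery-rate adjustment. The secondary mixed model has time, group and their interaction, with covariates as needed. Neither the testing nor the analysis section mentions practice effects, alternate test forms or the order of the aided and unaided runs.

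**The concern.** A follow-up score can exceed baseline for three reasons: the aid makes the signal clearer at that moment, months of wear have changed auditory processing (the reorganisation proposed in section 2.0, Treatment Options), or the participant has done the test before. Question d and Expected Outcome d concern the first and, by the protocol's own rationale, the second. The planned change from baseline adds the third to both.

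The delayed groups do not resolve this. Random assignment (section 5.2, Part 2) balances people, but the test schedule differs by arm, so the number of earlier runs differs by design. Any use of the mixed model's 0–6 month group contrast would carry that difference.

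The plan already collects a pair of scores, aided and unaided at one visit, in which person, date and elapsed time are fixed, but it specifies no inference on them. Because the follow-up score is not defined as aided or unaided, two different quantities could be reported under the same description and the choice could be made after the data are seen.

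**Working it through.** **1. Battery runs before the 6-month test** (section 5.1)

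| Occasion | Treated | Delayed |
|---|---|---|
| Before fitting / entry | 1 | 1 |
| 1 week | 2 (aided, unaided) | 0 |
| Months 1, 2, 4 | 0 | 0 |
| Part 2 total | 3 | 1 |
| CRTT and CRTT-R, adding 1 run in Part 1 | 4 | 2 |

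The excess is 3 − 1 = 4 − 2 = 2 runs. Before their own 12-month test the delayed groups will have had 1 + 1 + 2 = 4 Part 2 runs, or 1 + 2 = 3 if the battery is not repeated before fitting. On the planned primary endpoints, exposure is therefore similar across arms (3 against 3 or 4). The problem in those tests is that practice is present in all of them.

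**2. What each comparison contains.** Write A for the immediate effect of wearing the aid, L for learning from months of wear and P(k) for the practice gain after k earlier Part 2 runs. Treat these as additive for exposition.

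- Aided at 6 months − baseline, treated: A + L + P
- Unaided at 6 months − baseline, treated: L + P
- Aided − unaided, same visit: A + any order effect
- Treated − delayed change at 6 months, both unaided: L + [P(3) − P(1)]

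Only the third isolates A, and only if run order is balanced.

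**3. The plan's own figure.** Section 5.6 gives a detectable paired effect of 0.50 with power 0.80 at two-sided 0.01. For a paired t-test the noncentrality is d√n with n − 1 degrees of freedom.

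- n = 50: 0.50 × √50 = 3.54, power 0.799. The figure is reproduced.
- n = 25: 0.50 × √25 = 2.50, power 0.402; the detectable effect is 0.735.

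The stated 0.50 thus fits two pooled groups of 25. The number of pairs is not given.

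**4. Size of the unequal exposure, if a 0–6 month between-arm contrast were used.** The documents give no practice effect. Let b be the assumed value of the extra practice, in SD of the score compared, with no true aid effect. For a two-sample t-test the noncentrality is b√(n/2) with 2n − 2 degrees of freedom. At n = 50 and b = 0.2 it is 0.2 × √25 = 1.0.

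Chance of a significant result:

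| b | 25 v 25, 0.01 | 25 v 25, 0.05 | 50 v 50, 0.01 | 50 v 50, 0.05 |
|---|---|---|---|---|
| 0 | 1.0% | 5.0% | 1.0% | 5.0% |
| 0.1 | 1.4% | 6.4% | 2.0% | 7.9% |
| 0.2 | 3.0% | 10.7% | 5.6% | 16.8% |
| 0.4 | 11.3% | 28.3% | 27.1% | 50.8% |

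Both levels are shown because section 5.6 tests at 0.05 with false-discovery-rate adjustment but states power at 0.01. The 50 v 50 case pools both treated and both delayed groups, as sections 5.2 and 5.6 allow with four groups of 25.

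**5. Practice alone in the planned paired tests.** Here the whole practice gain since baseline counts, in SD of the within-person change. An assumed gain of 0.2 gives a significant result 5.0% (n = 25) or 11.3% (n = 50) of the time at 0.01, and 16.1% or 28.4% at 0.05. At 0.4 the figures are 23.8% or 56.2% at 0.01, and 48.4% or 79.2% at 0.05.

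**The case against.** A reader might infer that the plan's main analysis is a treated-versus-delayed test at 6 months and that it is biased. The documents do not support that. No such test is named, the primary behavioural tests are within group, and the mixed model is secondary and not restricted to months 0–6. The delayed groups' month-6 battery is itself an inference from section 5.1. If it is not given, there is no behavioural control score at 6 months to compare.

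Three other strong readings also fail.

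- That the paired scores go entirely unused: descriptive statistics cover all measurements, and an undefined single-subject metric is to examine individual responses. What is absent is a specified inferential contrast.
- That run order is unbalanced: the documents are silent on order.
- That a practice effect of a given size exists: it could be zero or could plateau. All participants have already met the CRTT and CRTT-R in Part 1, and the reading version could serve as a partial check on general retest gain, although no such analysis is named. Nor should an assumed between-arm bias be read against the plan's 0.50, which is a paired effect; the detectable between-arm effect at 0.01 is 0.695 (50 v 50) or 1.00 (25 v 25).

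It is also fair to say that the same-visit contrast misses any benefit that builds with wear, and that section 5.2 calls Part 2 preliminary and not a randomised controlled trial. This limits the seriousness of the point. It does not remove it: section 3.0 says the study is to support a larger intervention study, and the planned tests still cannot say what caused a change.

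**Conclusion.** The point holds in a limited form. Exposure to the battery before month 6 is 3 v 1 within Part 2 (4 v 2 for CRTT and CRTT-R overall). The primary paired changes contain practice in every arm, the group-by-time model has nothing to separate it, and the follow-up score is not defined as aided or unaided. Following the plan as written, a behavioural gain could not be attributed to amplification.

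The size of the resulting error is unknown. The 6–27% (nominal 0.01) and 17–51% (nominal 0.05) for 50 v 50, and 3–11% and 11–28% for 25 v 25, rest on an assumed 0.2–0.4 SD for the extra practice, no true aid effect, and a between-arm 6-month contrast that the plan permits but does not name. The point merits correction because the better comparison uses tests already scheduled.

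**What to change.** In section 5.6 (Part 2, Primary Analyses), add the paired aided-minus-unaided difference at 1 week and at 6 months as the test of immediate amplification benefit for the CCT, CRTT and phonetic context task. Under the plan's criteria (two-sided 0.01, power 0.80) it can detect a within-pair effect of 0.50 with the 50 treated participants pooled, or 0.735 within one group of 25.

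In section 5.1 (Follow-up Testing), randomise or counterbalance the order of the aided and unaided runs within each visit.

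In section 5.6, report the unaided change from baseline separately and describe it as perceptual learning plus practice. State that any treated-versus-delayed behavioural difference at 6 months includes unequal test exposure.

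The cost is analysis wording and a test-order list; no visits or tests are added. The limitation is that the same-visit contrast measures only the immediate effect of wearing the aid, so it complements the longitudinal change and does not replace it. Adding one run of the battery for the delayed groups at month 1 is not recommended: exposure would still be 3 v 2, and a home visit intended to reduce burden would have to move to the laboratory.
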